6.6.1.6 Treatments (study treatment, concomitant therapies)

The Safety set will be used for the following analyses.

Investigational treatment

Duration of study treatment, cumulative dose, average daily dose, actual dose intensity and relative dose intensity of each of the components of study treatment will be summarized and for every 28-day cycle. The number of patients with dose changes/interruptions will be, along with the reasons for the dose change/interruptions.

Concomitant treatments

Concomitant medications or procedures and significant non-drug therapies taken concurrently with the study treatment will be listed and summarized by WHO Anatomical Therapeutic Chemical (ATC) Class, Preferred Term. These summaries will include medications starting on or after the start of study treatment (defined as cycle 1 day 1) or medications starting prior to the start of study treatment and continuing after the start of study treatment. Any prior medication or significant non-drug therapy starting and ending prior to the start of study treatment will be listed.

For the analyses of transfusions, only transfusions received after start of study treatment and up to 30 days after last dose will be considered. The number of patients with transfusions and number of transfusions per patient will be analyzed.

6.6.1.7 Planned Data Displays

Data displays below present an indicative list of templates for the tables and figures that will be produced.

The following data displays are based on dummy data.

Table 2: Descriptive Analysis of Continuous Variables

		Groups	
		Group A	Group B
VAR1	Mean		
	SD		
	Q1		

Health Data Specialists	
DARE (EAE-2017/MM02)- Statistical Analysis Plan	Version: 1.0 EN
Author: GC, Reviewer: MS, Quality Assurance: GK	Date: 02-02-2018

	median		
	Q4		
	Min		
	Max		
	N		
<hr/>			
VAR2	Mean		
	SD		
	Q1		
	median		
	Q4		
	Min		
	Max		
	N		
<hr/>			
...			

Health Data Specialists	
DARE (EAE-2017/MM02)- Statistical Analysis Plan	Version: 1.0 EN
Author: GC, Reviewer: MS, Quality Assurance: GK	Date: 02-02-2018

Table 3: Descriptive Analysis of Categorical Variables

		Groups			
		Group A		Group B	
		N	%	N	%
VAR1	Level1				
	Level2				
	Level3				
VAR2	Level1				
	Level2				
...					

Table 4. Test statistics for categorical variables

		Cohort						P-value	
		Cohort A			Cohort B				
		N	%	95% CI	N	%	95% CI		
VAR1	Level1								
	Level2								
	Level3								
VAR2	Level1								
	Level2								
...									

Table 5. Test statistics for continuous variables – T-test/Mann-Whitney

		Group	
		Group A	Group B
VAR1	Mean		
	sd		
	Q1		
	median		
	Q4		
	Min		
	Max		
	N		

Health Data Specialists	
DARE (EAE-2017/MM02)- Statistical Analysis Plan	Version: 1.0 EN
Author: GC, Reviewer: MS, Quality Assurance: GK	Date: 02-02-2018

	P-value		
VAR2	Mean		
	sd		
	Q1		
	median		
	Q4		
	Min		
	Max		
	N		
	P-value		
...			

6.7 References

1. Rajan, A. M., and S. V. Rajkumar. "Interpretation of cytogenetic results in multiple myeloma for clinical practice." *Blood cancer journal* 5.10 (2015): e365.

Health Data Specialists	
DARE (EAE-2017/MM02)- Statistical Analysis Plan	Version: 1.0 EN
Author: GC, Reviewer: MS, Quality Assurance: GK	Date: 02-02-2018

APPENDIX 1

Table 6. Modified International Myeloma Working Group (IMWG) Uniform Response Criteria for Multiple Myeloma

Response	IMWG criteria
Stringent complete response (sCR)	CR as defined below plus normal FLC ratio and absence of clonal cells in bone marrow ¹ by immunohistochemistry or immunofluorescence. ²
Complete response (CR)	Negative immunofixation on serum and urine and disappearance of any soft tissue plasmacytomas and < 5% plasma cells in bone marrow. ¹
Very good partial response (VGPR)	Serum and urine M-protein detectable by immunofixation but not on electrophoresis or $\geq 90\%$ reduction in serum M-protein plus urine M-protein level $< 100 \text{ mg/24 h}$
Partial response (PR)	$\geq 50\%$ reduction of serum M-protein and reduction in 24 hours urinary M-protein by $\geq 90\%$ or to $< 200 \text{ mg/24 h}$. If serum and urine M-protein are unmeasurable, ³ a $\geq 50\%$ decrease in the difference between involved and uninvolved FLC levels is required in place of the M-protein criteria. If serum and urine M-protein are not measurable, and serum free light assay is also not measurable, $\geq 50\%$ reduction in plasma cells is required in place of M-protein, provided baseline bone marrow plasma cell percentage was $\geq 30\%$. In addition to the above listed criteria, if present at baseline, a $\geq 50\%$ reduction in the size of soft tissue plasmacytomas is also required.
Minor (Minimal) Response (MR)	25-49% reduction of serum M-protein and reduction in 24-hour urine M-protein by 50-89%, which still exceeds 200 mg per 24 hours. In addition, if present at baseline, 25-49% reduction in the size of soft tissue plasmacytomas is also required. No increase in the size or number of lytic bone lesions (development of compression fracture does not exclude response).
No change/Stable disease (SD)	Not meeting criteria for CR, VGPR, PR, or progressive disease.
Progressive disease (PD) ³	Any of the following: 
 • Increase of $\geq 25\%$ from lowest response value in any one or more of the following: 
 ◦ Serum M-component and/or (the absolute increase must be $\geq 0.5 \text{ g/dL}$)⁴ ◦ Urine M-component and/or (the absolute increase must be $\geq 200 \text{ mg/24 h}$) ◦ Only in patients without measurable serum and urine M-protein levels; the difference between involved and uninvolved FLC levels. The absolute increase must be $> 10 \text{ mg/dL}$ ◦ Bone marrow plasma cell percentage; the absolute percentage must be $\geq 10\%$⁵ • Definite development of new bone lesions or soft tissue plasmacytomas or definite increase in the size of existing bone lesions or soft tissue plasmacytomas • Development of hypercalcemia (corrected serum calcium $> 11.5 \text{ mg/dL}$ or 2.87 mmol/L) that can be attributed solely to the plasma cell proliferative disorder
Relapse	Clinical relapse requires one or more of: Direct indicators of increasing disease and/or end organ dysfunction (CRAB

Health Data Specialists	
DARE (EAE-2017/MM02)- Statistical Analysis Plan	Version: 1.0 EN
Author: GC, Reviewer: MS, Quality Assurance: GK	Date: 02-02-2018

	
features).⁴ It is not used in calculation of time to progression or progression-free survival but is listed here as something that can be reported optionally or for use in clinical practice
 
 • Development of new soft tissue plasmacytomas or bone lesions • Definite increase in the size of existing plasmacytomas or bone lesions. A definite increase is defined as a 50% (and at least 1 cm) increase as measured serially by the sum of the products of the cross-diameters of the measurable lesion • Hypercalcemia ($> 11.5 \text{ mg/dL}$) [2.87 mmol/L] • Decrease in hemoglobin of $\geq 2 \text{ g/dL}$ [1.24 mmol/L] • Rise in serum creatinine by 2 mg/dL or more [$177 \mu\text{mol/L}$ or more]
Relapse from CR ³ (To be used only if the end point studied is DFS) ⁶	
Any one or more of the following:
 
 • Reappearance of serum or urine M-protein by immunofixation or electrophoresis • Development of $\geq 5\%$ plasma cells in the bone marrow⁵ • Appearance of any other sign of progression (i.e., new plasmacytoma, lytic bone lesion, or hypercalcemia)

APPENDIX 2

Table 7. IMWG Renal Response Criteria

Criteria for the Definition of Renal Response to Antimyeloma Therapy		
Renal Response	Baseline eGFR, mL/min/1.73 m ² *	Best eGFR Response mL/min/1.73 m ²
Complete response	<50	≥ 60
Partial response	< 15	30-59
Minor response	<15 15-29	15-29 30-59

Abbreviations: CrCl, creatinine clearance; eGFR, estimate glomerular filtration rate.

*eGFR is based on the Modification of Diet in Renal Disease formula, or the Chronic Kidney Disease Epidemiology Collaboration equation.

Health Data Specialists	
DARE (EAE-2017/MM02)- Statistical Analysis Plan	Version: 1.0 EN
Author: GC, Reviewer: MS, Quality Assurance: GK	Date: 02-02-2018

Table 8. Simplified renal response criteria

Simplified criteria	Renal Response criteria
• Patients who presented with stage 5 RI (eGFR < 15 ml/min/1.73 m ²)should double their eGFR and improve to at least stage 4	
• Patients with stage 4 (eGFR 15-29 ml/min/1.73 m ²), increase their eGFR by at least 50% and improve to at least stage 3 (GFR \geq 60 mL/min/1.73 m ²)	
• Patients with stage 3 (eGFR 30-59 ml/min/1.73 m ²), increase their eGFR by at least 50% and improve to at least stage 2 (GFR \geq 60 mL/min/1.73 m ²)

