## Appendix 4 – Modified International Myeloma Working Group (IMWG) Uniform Response Criteria for Multiple Myeloma

Response	IMWG criteria
Stringent complete response (sCR)	CR as defined below plus normal FLC ratio and absence of clonal cells in bone marrow  by immunohistochemistry or immunofluorescence. 
Complete response (CR)	Negative immunofixation on serum and urine and disappearance of any soft tissue plasmacytomas and < 5% plasma cells in bone marrow. 
Very good partial response (VGPR)	Serum and urine M-protein detectable by immunofixation but not on electrophoresis or $\geq 90\%$ reduction in serum M-protein plus urine M-protein level < 100 mg/24 h
Partial response (PR)	$\geq 50\%$ reduction of serum M-protein and reduction in 24 hours urinary M-protein by $\geq 90\%$ or to < 200 mg/24 h. If serum and urine M-protein are unmeasurable,  a $\geq 50\%$ decrease in the difference between involved and uninvolved FLC levels is required in place of the M-protein criteria. If serum and urine M-protein are not measurable, and serum free light assay is also not measurable, $\geq 50\%$ reduction in plasma cells is required in place of M-protein, provided baseline bone marrow plasma cell percentage was $\geq 30\%$ . In addition to the above listed criteria, if present at baseline, a $\geq 50\%$ reduction in the size of soft tissue plasmacytomas is also required.
Minor (Minimal) Response (MR)	25-49% reduction of serum M-protein and reduction in 24-hour urine M-protein by 50-89%, which still exceeds 200 mg per 24 hours. In addition, if present at baseline, 25-49% reduction in the size of soft tissue plasmacytomas is also required. No increase in the size or number of lytic bone lesions (development of compression fracture does not exclude response).
No change/Stable disease (SD)	Not meeting criteria for CR, VGPR, PR, or progressive disease.

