6.6.1.4 Secondary Endpoint Analysis

All secondary efficacy analyses will be performed based on the FAS.

Overall Response Rate (ORR)

ORR is defined as the proportion enrolled subjects who achieve a best response of partial response (PR) or better using the Modified criteria of the IMWG (

Rajan, A. M., and S. V. Rajkumar. "Interpretation of cytogenetic results in multiple myeloma for clinical practice." *Blood cancer journal* 5.10 (2015): e365.

Health Data Specialists	
DARE (EAE-2017/MM02)- Statistical Analysis Plan	Version: 1.0 EN
Author: GC, Reviewer: MS, Quality Assurance: GK	Date: 02-02-2018

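### VGPR alone among the response categories carries no soft tissue plasmacytoma condition, so a patient whose baseline plasmacytoma falls short of the PR reduction can still count in ORR

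*SAP*

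**What the plan says.** SAP Appendix 1, Table 6, gives the response criteria row by row.

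- **CR** requires "disappearance of any soft tissue plasmacytomas"; sCR builds on CR and so inherits this.
- **VGPR** reads "Serum and urine M-protein detectable by immunofixation but not on electrophoresis or" a fall of at least 90%, worded as "reduction in serum M-protein plus urine M-protein level" below 100 mg/24 h. Nothing in the row concerns plasmacytomas.
- **PR** sets M-protein conditions and then adds a sentence beginning "In addition to the above listed criteria, if present at baseline, a", which asks for a reduction of at least 50% in plasmacytoma size.
- **MR** adds: "In addition, if present at baseline, 25-49% reduction in the size of soft tissue plasmacytomas is also required".
- **SD** is the residual category: "Not meeting criteria for CR, VGPR, PR, or progressive disease".

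Protocol Appendix 4 has the same rows. Its PR row ends "reduction in the size of soft tissue plasmacytomas is also required", and its VGPR row again has no such condition. Its note on VGPR in disease measurable only by free light chains (FLC) adds none either.

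SAP 6.6.1.4 and Protocol 10.4.3 define ORR as the proportion who "achieve a best response of partial response (PR) or better", so VGPR counts. DoR is restricted to the same patients.

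**The concern.** The categories are ordered, but the plasmacytoma requirement is not. It appears at MR, tightens at PR, vanishes at VGPR and returns at CR. A patient can therefore fail PR because of the plasmacytoma and still qualify for the better category, VGPR, and be counted in ORR.

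Patients with a plasmacytoma can enter: a biopsy-proven plasmacytoma is one way to meet the diagnostic criterion (Protocol 5.1), and Protocol 7.1.1.4 provides for imaging one that is present at baseline. At stake are the ORR estimate and the membership of the DoR analysis. With a single arm, no control rate exists in which the same misclassification would cancel.

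**Working it through.** The plan states no ORR target, power or sample size that depends on these definitions, so there is no figure to reproduce. The check is one of logic, followed by simple arithmetic.

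**1. The rows side by side** (SAP Table 6; Protocol Appendix 4 agrees)

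| Category | Main M-protein condition | Plasmacytoma, if present at baseline |
|---|---|---|
| CR | Immunofixation negative in serum and urine (plus marrow plasma cells < 5%) | Gone |
| VGPR | Serum down ≥ 90% and urine < 100 mg/24 h, or M-protein seen on immunofixation only | None stated |
| PR | Serum down ≥ 50%, urine down ≥ 90% or < 200 mg/24 h | Down ≥ 50% |
| MR | Serum down 25–49%, urine down 50–89% and still > 200 mg/24 h | Down 25–49% |

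**2. Test patients**, each with a baseline plasmacytoma, urine M-protein 50 mg/24 h (down 95%), positive immunofixation and no progression

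| Serum M-protein | Plasmacytoma | Rows met | In ORR? |
|---|---|---|---|
| −92% | −50% or more | VGPR and PR | Yes |
| −92% | −30% | VGPR only | Yes |
| −92% | 0% | VGPR only | Yes |
| −60% | −50% | PR | Yes |
| −60% | −30% | None, so SD | No |
| −60% | 0% | None, so SD | No |

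With the lesion held at −30% or 0%, the deeper M-protein fall alone turns a non-responder into a responder.

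**3. Direction.** The VGPR M-protein conditions are at least as strict as those for PR (≥ 90% implies ≥ 50%; < 100 mg/24 h implies < 200 mg/24 h). A VGPR patient whose plasmacytoma has shrunk by at least 50% therefore also meets PR and stays in ORR under either rule. Adding the condition to VGPR removes only patients who fail it. The present wording can add responders and cannot remove any.

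**4. Size.** The planned n is 38, so each such patient adds 1/38 = 2.6 points. To show the effect with an assumed count, using exact 95% intervals as the plan specifies:

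- 12/38 = 31.6% (17.5 to 48.7)
- 11/38 = 28.9% (15.4 to 45.9)

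The documents do not say how many patients have a baseline plasmacytoma. I assume 5–20% of 38 (38 × 0.05 = 1.9 and 38 × 0.20 = 7.6, so about 2 to 8 patients), of whom 5–15% meet VGPR on M-protein without a 50% lesion reduction:

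- low: 2 × 0.05 = 0.1 patients, 0.1/38 = 0.3 points
- high: 8 × 0.15 = 1.2 patients, 1.2/38 = 3.2 points

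**5. What is and is not touched.** PFS uses the PD row and death, and neither refers to VGPR. ORR and entry to DoR both use PR or better, so both are touched. Confirmation does not repair the gap: Protocol 7.1.1 has response confirmed through M-protein assessments.

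**The case against.** The strongest reply is that the ladder is meant to be nested. Protocol 7.1.1 treats VGPR as a better category than PR, lets a later VGPR confirm an earlier PR, and has the investigator assess response using imaging as well as M-protein. Plasmacytomas are assessed clinically on day one of each cycle (Table 7.1). An investigator might well not score an unchanged plasmacytoma as VGPR. This stands in part: neither document says that response is derived by program from the table, so it is not certain that such patients would be counted. But no passage states the nesting. CR, PR and MR each carry their own plasmacytoma condition, and the PR sentence sits inside the PR row. Ranking VGPR above PR is what makes the omission matter.

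A second reply is that the table is presented as the adopted modified IMWG criteria. Whether the VGPR row departs from its source cannot be checked from the documents. That is a reason to label the change as a clarification, not to leave the scoring open.

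A third is that the effect is small beside an interval about 31 points wide (48.7 − 17.5) on a secondary endpoint with no hypothesis attached. That is correct and limits the weight of the point.

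A reader might also infer more than the documents support:

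- **That the VGPR rate is a biased endpoint.** It is not a listed endpoint in either document.
- **That a lesion grown by up to 49% counts as a response under the SAP.** The 50% progression threshold is in the PD row of Protocol Appendix 4. The SAP's PD row speaks only of a definite increase, without a figure.
- **That DoR starts about two months too early in every such patient.** A VGPR can be recorded at Cycle 2 Day 1 (week 4), and the first 12-weekly scan comes 8 weeks later. But a patient whose lesion had truly shrunk by week 4 has the right start date, and dating response at the scan would then start DoR late.

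**Conclusion.** The point holds. As written, SAP Table 6 and Protocol Appendix 4 score the same insufficiently reduced plasmacytoma as disqualifying at PR and irrelevant at VGPR. The rule gives an inconsistent result; it is not merely short of detail.

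The error in ORR has a known direction, upward, and each affected patient is worth 2.6 points. Under the assumed rates the number affected is 0.1 to 1.2, in practice none or one; both rates are assumptions without support in the documents. The effect extends to who enters DoR. The primary endpoint, PFS, is unaffected. The rule should be settled before the analysis, so that who counts as a responder is not decided after the data are seen.

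**What to change.** **Change.** In the VGPR row of SAP Table 6 and of Protocol Appendix 4, add that if a soft tissue plasmacytoma was present at baseline, the PR reduction (at least 50%) is also required. Word it so that it also covers the protocol's FLC-only definition of VGPR. Add a footnote that this clarifies the adopted IMWG table. State in SAP 6.6.1.4 that ORR and the DoR population follow this rule.

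**Imaging.** Do not require response to be dated at the scan. Protocol 7.1.1.4 calls for CT/MRI every 12 weeks when a plasmacytoma was present at baseline, whereas Protocol Tables 7.1 and 7.2 and SAP Table 1 provide for CT/MRI after screening only as clinically indicated. These passages must be reconciled. Making a scan a condition of every response could turn unscanned patients into non-responders and could start DoR late. Instead, list patients with a baseline plasmacytoma who have no repeat imaging.

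**Cost.** One sentence and a footnote in each table, one statement in SAP 6.6.1.4 and one listing. ORR may come out slightly lower, and the VGPR row will carry wording that the adopted table, as reproduced in these documents, does not have.
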